5.6 Dose Modification

No dose modification will be made for Grade 1 adverse events.

For Grade 2 adverse events not considered related to study agent persisting until the next scheduled injection of vaccine, the scheduled injection may be given or omitted at the discretion of the study physician.

For Grade 2 or 3 adverse events definitely, probably or possibly related to study agent persisting until the next scheduled injection of vaccine, the scheduled injection will be omitted. Participants will receive subsequent doses of study agent when toxicity is resolved to Grade 1 or less.

For Grade 3 adverse events unrelated or unlikely related to study agent persisting until the next scheduled injection of vaccine, the scheduled injection will be omitted. Participants will receive subsequent doses of study agent when toxicity is resolved to Grade 2 or less.

For Grade 4 events unrelated or unlikely related to study agent persisting until the next scheduled injection of vaccine, the scheduled injection will be omitted. Participants may receive subsequent doses of study agent when toxicity has resolved to Grade 2 or less, at the discretion of the study physician. Participants with Grade 4 events that are definitely, probably or possibly related to the study agent will receive no further doses of vaccine/placebo and be followed for resolution of adverse events. If appropriate, they should remain on-study and undergo the post-intervention biopsy.

Vaccine injections may be held at the discretion of the patient and/or investigator for any concerns related to drug toxicity.

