In a randomized, controlled, and blinded Phase 2 study, PROSTVAC-VF treatment was evaluated for safety and for prolongation of progression-free survival (PFS) and overall survival (OS) [14]. In total, 125 patients were randomly assigned at multiple centers. Eligible patients had minimally symptomatic mCRPC. A vaccinia-based vector was used for priming followed by six planned fowlpox-based vector boosts. Patients were allocated (2:1) to PROSTVAC-VF plus GM-CSF or to control empty vectors plus saline injections. Eighty-two patients received PROSTVAC-VF and 40 received control vectors. Patient characteristics were

similar in both groups. In general PROSTVAC was well tolerated. Most AEs were injection site reactions with only a subset of patients experiencing associated systemic AEs such as fatigue, fevers, and nausea. Typical injection site reactions were mild, with only one clear grade 3 injection site reaction (injection site cellulitis). The AE profile of primary vaccinia immunization was equivalent to that induced by the fowlpox booster immunizations. Two PROSTVAC-treated patients discontinued therapy because of treatment-related AEs. One had recurrent lip edema after the second and third vaccinations; the other developed multiple AEs and SAEs associated with thrombotic thrombocytopenic purpura and myocardial infarction. The case was reported as possibly related to treatment. Thrombotic thrombocytopenic purpura has not been reported in association with vaccinia immunization [24].

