A 3+3 Phase 1 dose-escalation study design of intraprostatic administration of PSA-TRICOM vaccine was performed in patients with locally recurrent or progressive prostate cancer [25]. Nineteen of 21 patients enrolled had locally recurrent prostate cancer after definitive radiation therapy, while two had no prior local therapy. All cohorts received initial subcutaneous vaccination with recombinant vaccinia (rV)-PSA-TRICOM and then intraprostatic booster vaccinations with recombinant fowlpox (rF)-PSA-TRICOM. Cohorts 3–5 also received intraprostatic rF-GM-CSF. Cohort 5 received additional subcutaneous boosters with rF-PSA-TRICOM and rF-GM-CSF. There were no DLTs, and the maximum tolerated dose was not reached. Twenty of 21 patients received all planned doses of vaccine, and no patient was discontinued for toxicity. The most common toxicity, subcutaneous injection site reaction, occurred with 47 % of administered doses. Fever, the second most common toxicity, occurred in 40.2 % of all treatment cycles. The most common grade 2 AEs were fever (38 %) and subcutaneous injection site reactions (33 %); the single grade 3 event was transient fever. Fevers generally occurred within hours of receiving the vaccine. None was serious enough to require intervention beyond acetaminophen, and all were transient.

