A Phase I dose-escalation trial was performed to assess the safety and tolerability of escalating doses of ipilimumab in combination with a fixed dose of the PSA-Tricom vaccine [23]. Thirty patients with mCRPC received 2×10^8 plaque-forming units of recombinant vaccinia PSA-Tricom subcutaneously on day 1 of cycle 1, with subsequent monthly boosts of 1×10^9 plaque-forming units, starting on day 15. Intravenous ipilimumab was given monthly starting at day 15, at doses of 1, 3, 5, and 10 mg/kg. Twenty-four of the patients had not previously been treated with chemotherapy. A DLT for the vaccine and antibody combination was not identified during the period two weeks after the second infusion of ipilimumab. AEs were primarily local grade 1 and 2 injection-site reactions (three patients with grade 1 events, 26 with grade 2) and immune-related AEs. Rash was the most common immune-related AE, noted mostly in patients receiving 10 mg/ipilimumab kg. Endocrine immune-related AEs were more common at 5 and 10 mg/kg doses. However, grade 2 and 3 diarrhea or colitis were consistently noted at all doses beyond the lowest (1 mg/kg). Other uncommon immune-related AEs included raised concentrations of aminotransferases and neutropenia or leukopenia. Overall, 21 patients (70%) had a grade 2 or greater immune-related AE, and eight patients (27%) had grade 3 or 4 immune-related AEs.

There were no other non-immune-related grade 4 toxic effects, and the remaining grade 3 toxic effects were probably related to the accompanying immune-related AEs in the same patient, including dehydration (two patients), hypotension (two patients), fatigue (two patients), hyponatraemia (one), hypophosphataemia (one), and fever (one). One grade 3 thrombocytopenia occurred in a patient with colitis.

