11.1 Adverse Events

11.1.1 Reportable AEs

All AEs that occur after the informed consent is signed and baseline assessments are completed (including run-in) must be recorded on the AE CRF (paper and/or electronic) whether or not related to study agent.

11.1.2 AE Data Elements:

The following data elements are required for adverse event reporting.

- AE verbatim term
- System Organ Class (SOC)
- Common Terminology Criteria for Adverse Events v4.0 (CTCAE) AE term
- Event onset date and event ended date
- Severity grade
- Attribution to study agent (relatedness)
- Whether or not the event was reported as a serious adverse event (SAE)
- Whether or not the subject dropped due to the event
- Outcome of the event

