For both primary and secondary endpoints, data will be tested for non-normality and outliers. If the normality assumption is violated, a potential transformation will be sought. If no suitable transformations can be found, nonparametric tests (e.g. Wilcoxon Rank Sum test and Spearman correlation coefficient) will be used. If outliers are detected, sensitivity analysis will be performed to evaluate the impact of the outliers on the effects of PROSTVAC®. In addition, we anticipate observing a missing rate of 25% or greater for both primary and secondary endpoints. The missing rates for both PROSTVAC® and placebo groups will be reported and compared. Also, regression models will be performed to identify the potential variables that are predictive of the missing endpoints or probabilities.

Descriptive statistics of the type and frequency of all adverse events will be generated, including 95% confidence intervals. For each type of the adverse events, a Fisher's exact test will be performed to compare the frequency of the adverse event between the two groups.

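### Section 13.5 compares adverse events between arms only by a Fisher's exact test per event type; for injection-site reactions, two cheap exploratory additions would also use recurrence and grade (minor)

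*Combined protocol and SAP*

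**What the plan says.** The adverse-event analysis is two sentences at the end of section 13.5. The first is descriptive: "Descriptive statistics of the type and frequency of all adverse events will be generated, including 95% confidence intervals". The second says that, for each event type, a Fisher's "exact test will be performed to compare the frequency of the adverse event between the two groups". Sections 13.6 to 13.9 add no analysis by grade, recurrence or dose. Section 13.5 also lists safety and feasibility among the secondary endpoints and gives a two-sample t test for the secondary endpoints, but no numeric safety variable is defined, so that sentence yields no usable adverse-event comparison.

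Section 11.1.2 requires more than occurrence for every event. Its list includes "Severity grade", relatedness to study agent, and onset and end dates. Section 5.6 uses grade and relatedness for dosing: for Grade 2 or 3 events "definitely, probably or possibly related to study agent persisting until the next scheduled injection of vaccine, the scheduled injection will be omitted".

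Each man is scheduled for one priming and six booster injections (section 5.1), and the placebo is empty vector on the same schedule (section 5.2). Safety and feasibility in the active surveillance population is secondary objective 1.2.12.

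**The concern.** Fisher's test needs one independent yes/no per man, so the workable meaning of frequency here is whether the man ever had the event. A man with one Grade 1 site reaction then counts the same as a man who reacts to all seven injections or has a Grade 2 reaction.

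For most event types this matters little. Injection-site reactions differ because there are seven chances to react and the control injection may itself cause reactions. If most men in both arms react at least once, the ever/never variable is near its ceiling and has little room to show a difference. What could be missed is whether PROSTVAC causes more repeated, or more severe, local reactions than empty vector. The designers of a later prevention trial in low-risk men would want to know that.

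**Working it through.** **Plan's own figure.** The documents give no power for any adverse-event comparison, so there is none to reproduce.

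**Inputs from the documents.** Arms are 100 v 50 (section 13.2), and all men are evaluable for toxicity from first dose (section 13.7). There are 1 + 6 = 7 scheduled injections. Evidence on rates is indirect and comes from section 6.2:
- Phase 1 study with intraprostatic boosters: "The most common toxicity, subcutaneous injection site reaction, occurred with 47 % of administered doses".
- Ipilimumab combination study of 30 patients: "local grade 1 and 2 injection-site reactions (three patients with grade 1 events, 26 with grade 2"), so any grade is 29/30 = 96.7% and Grade 2 is 26/30 = 86.7%.
- The randomized trial closest in design, with GM-CSF in its active arm: "Typical injection site reactions were mild, with only one clear grade 3 injection site reaction (injection site cellulitis"). No rate by arm is given.

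**Assumptions.** Two-sided 5% level (none is stated for these tests), the placebo rate, the within-man correlation (ICC 0 to 0.5), the lower rates of 25% and 15% per dose, and transfer of the rates above to this regimen.

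**Step 1: the ceiling.** With independent doses, P(at least one reaction) = 1 − (1 − p)^7.
- PROSTVAC, p = 0.47: 1 − 0.53^7 = 98.8%.
- Placebo at ratio 0.7, p = 0.7 × 0.47 = 0.329: 1 − 0.671^7 = 93.9%.

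A gap of 14 percentage points per dose shrinks to 5 points on ever/never.

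**Step 2: recurrence.** Each man's reaction probability is drawn from a beta distribution with the stated ICC, then seven doses are simulated (3,000 runs at 47%, 1,500 at the lower rates). The planned Fisher test on any occurrence is compared with a tie-corrected Wilcoxon rank-sum test on reactions divided by injections given. Power at ICC 0 / 0.1 / 0.3 / 0.5, no doses omitted:

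| PROSTVAC per dose | Placebo/PROSTVAC ratio | Fisher, any occurrence (%) | Wilcoxon, reactions per injection (%) |
|---|---|---|---|
| 47% | 0.5 | 93 / 95 / 94 / 92 | 100 / 100 / 99 / 97 |
| 47% | 0.6 | 68 / 75 / 77 / 72 | 100 / 100 / 95 / 86 |
| 47% | 0.7 | 37 / 43 / 46 / 43 | 99 / 93 / 75 / 60 |
| 47% | 0.8 | 13 / 20 / 22 / 18 | 80 / 62 / 42 / 31 |
| 47% | 1.0 (no difference) | 1 / 3 / 3 / 4 | 4 / 4 / 4 / 4 |
| 25% | 0.7 | 43 / 39 / 30 / 25 | 79 / 59 / 40 / 31 |
| 15% | 0.7 | 35 / 29 / 23 / 17 | 52 / 38 / 27 / 19 |

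Repeat runs move these by a few points. With no difference, the Wilcoxon test rejected about 4–7% across runs, so the gain is not bought with a materially inflated error rate. Giving each reaction a 30% chance of causing the next dose to be omitted changes little: at 47% and ratio 0.7 the results are 37 / 42 / 47 / 44 against 99 / 90 / 73 / 61.

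**Step 3: severity only.** Exact Fisher power, equal any-grade rates in both arms:
- Any grade 96.7% in both arms; Grade ≥2 86.7% v 60 / 65 / 70 / 75%. The any-grade test rejects 2% of the time; Fisher on Grade ≥2 has 94 / 83 / 64 / 39% power.
- Any grade 80% in both arms; Grade ≥2 33% v 10 / 15 / 20%. The any-grade test rejects 4%; Fisher on Grade ≥2 has 90 / 65 / 35%.

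**Step 4: occurrence only, same severity mix.** Any grade 96.7% v 80 / 85 / 90%. The planned test has 89 / 68 / 35% power, against 56 / 33 / 14% for Grade ≥2. The Grade ≥2 test must therefore be added to the planned test and not replace it.

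**Step 5: Grade ≥3.** At 5% v 0% the power is 6%, so a test at that cut-off has no use here.

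**The case against.** One Fisher test per event type, with descriptive statistics and confidence intervals, is a conventional safety plan, and nothing in it is contradictory. It answers whether a man ever reacts. The Wilcoxon test answers how often, and no objective names recurrence. An ever/never test cannot see a severity-only difference by construction. All of that stands, and it is why this is an improvement to an exploratory analysis and not an error.

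The rates are also borrowed. The 47% comes from a study with mostly intraprostatic boosters and the 86.7% from a combination with ipilimumab, while the closest trial calls typical reactions mild. No document gives a placebo rate, and with empty vector the arms could be close to equal. This stands too. It makes recurrence the main issue and severity the lesser one, and it makes every power figure scenario-dependent. The 30% omission model is cruder than section 5.6, which changes nothing for Grade 1 and omits a dose for related Grade 2–3 events only if they persist; the results barely depend on it.

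A reader might infer that the planned test is invalid, that safety in this trial is unprotected, or that grade will go unreported. The documents support none of these. The test is valid on one yes/no per man; grade-based dosing rules, SAE reporting and the DSMB cover individual safety; and by-grade tables are unspecified, not excluded.

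**Conclusion.** The point holds as a cheap, minor improvement to an exploratory safety comparison, limited to injection-site reactions. If reactions are common (47% per dose) and the excess is moderate (ratio 0.7), the planned test has about 37–49% power and the per-injection Wilcoxon about 60–99%, from ICC 0.5 to 0, taken across runs. The gain is small at 15% per dose with ICC 0.3–0.5 (about 18–25% against 20–28%) and when the placebo rate is half (92–95% against 97–100%). For a severity-only difference the planned test rejects at its null rate of 2–4%.

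These figures rest on assumed placebo rates and clustering and on reaction rates from other regimens. It would go too far to say that the plan has low power for adverse events in general, or that PROSTVAC is expected to cause more local reactions than empty vector: the working covers one event class, and the documents give no rate by arm.

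**What to change.** In section 13.5 keep the Fisher test and state that it uses one yes/no, any occurrence, per man. Then add, for injection-site reactions only:

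- the number of reactions divided by the number of injections given, computed for each man and compared between arms by the Wilcoxon rank-sum test;
- the proportion of men with a Grade ≥2 reaction, compared by Fisher's exact test;
- a statement that both are exploratory and unadjusted.

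Dividing by injections given is needed because section 5.6 omits doses after persisting related Grade 2–3 events, so men with worse reactions may receive fewer injections and raw counts could understate the worse arm. Instruct sites to enter each reaction as a separate event. This may already happen, since onset and end dates are required, but the entry conventions are not in these documents.

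The cost is SAP wording, one data-entry instruction and two more unadjusted exploratory p-values. No patients, visits or procedures are added. Maximum-grade tables for other event types are optional reporting and not part of this change.

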13.6 Reporting and Exclusions

The reporting will be based on the intent-to-treat principle in which the intent-to-treat population will be used for data analysis and reporting.

Explanatory analyses will evaluate endpoints in those participants who received 2 or more doses of PROSTVAC-F (boost).

13.7 Evaluation of Toxicity

All participants will be evaluable for toxicity from the time of their first dose of study agent.

13.8 Evaluation of Response

Evaluation of response will be based on the intent-to-treat principle in which the intent-to-treat population will be used for data analysis.

Subanalyses may be performed on the subsets of participants, excluding those for whom major protocol deviations have been identified (e.g., early death due to other reasons, early discontinuation of intervention, major protocol violations, etc.). However, subanalyses may not serve as the basis for drawing conclusions concerning efficacy, and the reasons for excluding participants from the analysis should be clearly reported.

13.9 Interim Analysis

No formal interim analysis for futility is planned because the primary endpoints will be analyzed in batches at the end of the study. Accrual, data collection, and any adverse events will be monitored on a regular basis.

13.10 Ancillary Studies

None.

14. ETHICAL AND REGULATORY CONSIDERATIONS

14.1 Form FDA 1572

Prior to initiating this study, the Protocol Lead Investigator at the Lead or Participating Organization(s) will provide a signed Form FDA 1572 stating that the study will be conducted in compliance with regulations for clinical investigations and listing the investigators, at each site that will participate in the protocol. All personnel directly involved in the performance of procedures required by the protocol and the collection of data should be listed on Form FDA 1572.

14.2 Other Required Documents

14.2.1 Signed and dated current (within two years) CV or biosketch for all study personnel listed on the Form FDA 1572 and Delegation of Tasks form for the Lead Organization and all Participating Organizations.

14.2.2 Current medical licenses (where applicable) for all study personnel listed on Form FDA 1572 and Delegation of Tasks form for the Lead Organization and all Participating Organizations.

14.2.3 Lab certification (*e.g.*, CLIA, CAP) and lab normal ranges for all labs listed on Form FDA 1572 for the Lead Organization and all Participating Organizations.

14.2.4 Documentation of training in “Protection of Human Research Subjects” for all study personnel listed on the FDA Form 1572 and Delegation of Tasks form for the Lead Organization and all Participating Organizations.

14.2.5 Documentation of Federalwide Assurance (FWA) number for the Lead Organization and all Participating Organizations.

14.2.6 Signed Investigator’s Brochure/Package Insert acknowledgement form

14.2.7 Delegation of Tasks form for the Lead Organization and all Participating Organizations signed by the Principal Investigator for each site and initialed by all study personnel listed on the form

14.2.8 Signed and dated NCI, DCP Financial Disclosure Form for all study personnel listed on Form FDA 1572 for the Lead Organization and all Participating Organizations

14.3 Institutional Review Board Approval

Prior to initiating the study and receiving agent, the Investigators at the Lead Organization and the Participating Organization(s) must obtain written approval to conduct the study from the appropriate IRB. Should changes to the study become necessary, protocol amendments will be submitted to the DCP PIO according to DCP Amendment Guidelines. The DCP-approved amended protocol must be approved by the IRB prior to implementation

14.4 Informed Consent

All potential study participants will be given a copy of the IRB-approved Informed Consent to review. The investigator will explain all aspects of the study in lay language and answer all questions regarding the

study. If the participant decides to participate in the study, he/she will be asked to sign and date the Informed Consent document. The study agent(s) will not be released to a participant who has not signed the Informed Consent document. Subjects who refuse to participate or who withdraw from the study will be treated without prejudice.

Participants must be provided the option to allow the use of blood samples, other body fluids, and tissues obtained during testing, operative procedures, or other standard medical practices for further research purposes. If applicable, statement of this option may be included within the informed consent document or may be provided as an addendum to the consent.

Prior to study initiation, the informed consent document must be reviewed and approved by NCI, DCP, the Consortium Lead Organization, and the IRB at each Organization at which the protocol will be implemented. Any subsequent changes to the informed consent must be approved by NCI, DCP, the Consortium Lead Organization's IRB, and then submitted to each organization's IRB for approval prior to initiation.

14.6 Other

This trial will be conducted in compliance with the protocol, Good Clinical Practice (GCP), and the applicable regulatory requirements.

APPENDIX A

Performance Status Criteria

ECOG Performance Status Scale		Karnofsky Performance Scale	
Grade	Descriptions	Percent	Description
0	Normal activity. Fully active, able to carry on all pre-disease performance without restriction.	100	Normal, no complaints, no evidence of disease.
		90	Able to carry on normal activity; minor signs or symptoms of disease.
1	Symptoms, but ambulatory. Restricted in physically strenuous activity, but ambulatory and able to carry out work of a light or sedentary nature (e.g., light housework, office work).	80	Normal activity with effort; some signs or symptoms of disease.
		70	Cares for self, unable to carry on normal activity or to do active work.
2	In bed <50% of the time. Ambulatory and capable of all self-care, but unable to carry out any work activities. Up and about more than 50% of waking hours.	60	Requires occasional assistance, but is able to care for most of his/her needs.
		50	Requires considerable assistance and frequent medical care.
3	In bed >50% of the time. Capable of only limited self-care, confined to bed or chair more than 50% of waking hours.	40	Disabled, requires special care and assistance.
		30	Severely disabled, hospitalization indicated. Death not imminent.
4	100% bedridden. Completely disabled. Cannot carry on any self-care. Totally confined to bed or chair.	20	Very sick, hospitalization indicated. Death not imminent.
		10	Moribund, fatal processes progressing rapidly.
5	Dead.	0	Dead.
